Study **XL184-005** is a phase I, open-label, randomized, single-dose, two-treatment, two-way crossover comparative bioavailability study of cabozantinib tablet and capsule formulations in healthy volunteers. Subjects received single oral doses of the assigned treatment of Test (100 mg cabozantinib, dosed as one 100-mg tablet) or Reference (100 mg cabozantinib, dosed as two 50-mg capsules), according to a randomization scheme. Each dosing was administered under fasting conditions, and blood samples were collected up to 504 hours post-dose for each subject after each treatment to assess plasma cabozantinib PK. See [“Pharmacokinetics” section](#) for results.

In Study **XL184-008**, subjects with advanced solid tumors (particularly renal cell carcinoma [RCC] and differentiated thyroid cancer [DTC]) are evaluated for any potential clinically significant drug-drug interaction of cabozantinib on the CYP isozyme CYP2C8. The effect of qd dosing of 175 mg cabozantinib and a single dose of rosiglitazone will be evaluated. In 11 patients evaluated for AEs, the most common grade 3 or higher AEs were fatigue (9%), hypophosphatemia (27%), blood amylase increase (9%), and hyponatremia (9%).

In a phase I study, **CA205-001**, Japanese subjects with advanced or metastatic solid tumors for whom the standard of care is ineffective or inappropriate, received cabozantinib at a starting dose of 75 mg PO qd. Two of the three subjects in the first cohort experienced DLTs of proteinuria and thrombocytopenia. Because of a change in study sponsor, this study was reinitiated as **XL184-014**. One additional subject was enrolled as of May 2011 at 50 mg PO qd.

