#### Pharmacokinetics

Pharmacokinetic analysis of 74 subjects in trial **XL184-001** showed dose proportional increases in maximum plasma concentration ( $C_{max}$ ) and AUC both for PIB (dose range 0.08-11.52 mg/kg) and the capsule formulation (dose range: 125 to 175 mg) (Kurzrock, 2011). Terminal-phase half-life ( $t_{1/2,z}$ ) values were 59.1 to 136 hours (Investigator's Brochure, 2011). After repeat dosing,  $t_{1/2,z}$  values (mean  $\pm$  standard deviation) for cabozantinib were  $91.3 \pm 33.3$  hours ( $n = 23$ ), and apparent steady-state plasma levels were reached by Day 15 (Kurzrock, 2011). Steady-state clearance for the 175 mg capsule dose derived from repeat dose data was  $4.2 \pm 1.5$  L/h. Subjects who received 175 mg capsules had four- to five-fold higher steady-state exposure (AUC) compared with Day 1 ( $7.68 \pm 2.85$  mcg·h/mL;  $n = 23$  vs.  $41.6 \pm 15.3$  mcg·h/mL;  $n = 23$ ), indicating that cabozantinib accumulated with repeat daily dosing. There was no significant difference in exposure between patients with MTC and those without MTC.

Based on the preliminary PK data from 23 subjects in **XL184-005** who completed both treatments, after a single oral dose of cabozantinib at 100 mg, the terminal  $t_{1/2,z}$  of cabozantinib appeared to be similar for both tablet and capsule formulations, with approximately mean values of 110 hours (Exelixis Communication, 2012). The median time to the maximum plasma concentration ( $t_{max}$ ) was 4 hours for the tablet formulation and 5 hours for the capsule formulation. High inter-subject variability for  $C_{max}$  and the area under the plasma drug concentration time curve (AUC) values were observed for both formulations (coefficient of variation [CV] %  $C_{max}$ : 51% for the tablet formulation, 61% for the capsule formulation; CV% for the AUC from time zero to the last quantifiable timepoint or to infinity [ $AUC_{0-last}$  or  $AUC_{0-inf}$ ]: 40-43% for the tablet formulation, 43% for the capsule formulation). The geometric mean  $C_{max}$  of the tablet formulation was approximately 39% higher than the value observed for the capsule formulation. The geometric mean  $AUC_{0-last}$  and  $AUC_{0-inf}$  values for the tablet formulation were also higher (15% and 19%, respectively) than those observed for the capsule formulation. However, due to the high within-formulation variability observed, no statistical difference in exposure between the two formulations was apparent.

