**To permit pharmacokinetic sampling studies, AM dosing is required during the first cycle of therapy.** Blood samples will be collected prior to the initial AM cabozantinib dose and at 4 hours post-dose on Cycle 1 Day 1. Blood sampling for steady-state PK determinations will be collected during the dosing interval at pre-dose (Cycle 1, Day 22), 0.5, 1, 2, 4, 6, 8, and 24 hr (Cycle 1, Day 23). For the optional samples that are to be obtained at the time of disease progression or in the event of toxicity, a blood sample should be drawn as close as possible to the time of the event with documentation of the last cabozantinib dose administered. For each sample, at least 6 mL of whole blood will be collected in tubes or Vacutainers™ containing EDTA as an anticoagulant, kept on ice, and centrifuged within 30 min to isolate plasma. Plasma will be frozen in two to three aliquots immediately and stored at  $-70^{\circ}\text{C}$  (or less) protected from light for later analysis by the Analytical Pharmacology Core Laboratory at the Sidney Kimmel Comprehensive Cancer Center at Johns Hopkins University under the direction of [name] (See [Appendix IV](#) Pharmacokinetic (PK) Specimen Collection, Preparation and Shipping Instructions).

Samples will be measured using liquid chromatography/tandem mass spectrometric (LC/MS/MS) method in the Analytical Pharmacology Core

Laboratory at the Sidney Kimmel Comprehensive Cancer Center (SKCCC) at Johns Hopkins. Relevant individual PK parameters will be estimated using non-compartmental or compartmental PK methods with the software WinNonlin. For each Stratum, the pharmacokinetic variables will be tabulated and descriptive statistics (e.g., geometric means and coefficients of variation) calculated for each dose level. Pharmacokinetic parameters (i.e.,  $T_{1/2}$ ,  $Cl$ , and AUC) will be compared across relevant antiretroviral therapies using nonparametric statistical testing techniques. Correlations with toxicity and efficacy will be explored using nonparametric statistical testing techniques. Significance for comparisons will be at the  $p<0.05$  level.

10.1.2 To investigate the effects of therapy on participant immune status and HIV viral load.

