### **12.4 Analysis of Secondary Endpoints**

Secondary endpoints for this study include response rates and effects of therapy on HIV viral load and CD4+ and CD8+ cell counts, as well as the results of pharmacokinetic studies. For participants with measurable disease, response evaluations will occur at 2 cycle intervals via RECIST 1.1. Study treatment may continue indefinitely until one of the following criteria applies: 1) unacceptable toxicity (including DLT in cycle 1); 2) progressive disease; or 3) participant withdrawal or removal.

To investigate possible pharmacokinetic interactions between cabozantinib and antiretroviral therapy in persons with HIV infection, pharmacokinetic analysis calculations will be conducted using WinNonlin (Pharsight Corporation, Mountain View, CA) with noncompartmental or compartmental methods. Relevant pharmacokinetic parameters will be computed for cabozantinib and relevant metabolites. The pharmacokinetic variables will be tabulated and descriptive statistics (e.g., geometric means and coefficients of variation) calculated for each dose level. Pharmacokinetic parameters (i.e.,  $T_{1/2}$ , Cl, and AUC) will be compared across relevant antiretroviral therapies using nonparametric statistical testing techniques. Concentrations obtained from the time of disease progression and the time of a DLT or other persistent and severe toxicity will be treated as independent samples and summarized in a descriptive manner. Correlations with toxicity and efficacy will be assessed using nonparametric statistical testing techniques. Significance for comparisons will be at the  $p<0.05$  level.

To investigate the effects of cabozantinib on participant immune status and HIV viral load, trends in CD4+ and CD8+ counts and viral load determinations during trial participation will be evaluated. A repeated measures analysis of variance will be used to assess the effect of cabozantinib on CD4+ and CD8+ cell counts and HIV viral loads across time points. Analyses will be done per stratum, where the data are sufficient. If the data do not meet the assumptions of normality, Friedman's test, the nonparametric analogue to a repeated measures analysis of variance, will be used.

Collectively and over each stratum, binomial proportions and their 95% confidence intervals will be used to preliminarily assess response rates for single agent cabozantinib in malignancies for which at least 4 participants have been enrolled.

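### T1/2 is tested across antiretroviral groups at p<0.05, but a noncompartmental T1/2 is not reliably estimable from one 24 h steady-state dosing interval

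*Combined protocol and SAP*

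**What the plan says.** Secondary objective 1 (Section 1.2.1) is the pharmacokinetic interaction between cabozantinib and antiretroviral therapy. Section 12.4 states: "Pharmacokinetic parameters (i.e., $T_{1/2}$ , Cl, and AUC) will be compared across relevant antiretroviral therapies", with nonparametric tests. It sets the threshold as follows: "Significance for comparisons will be at the" p<0.05 level. Section 10.1.1 repeats both statements. Both sections allow noncompartmental or compartmental estimation and do not choose between them.

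On sampling, Section 10.1.1 states: "steady-state PK determinations will be collected during the dosing interval at pre-dose (Cycle 1, Day 22), 0.5, 1, 2, 4, 6, 8, and 24 hr". The last of these falls on Day 23. The only other scheduled samples are on the first day: "Blood samples will be collected prior to the initial AM cabozantinib dose and at 4 hours post-dose on Cycle 1 Day 1". Dosing is continuous, so no washout sample is scheduled. Samples requested at progression, DLT or severe toxicity are taken when feasible, and Section 12.4 limits them to descriptive summary.

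On the half-life, the Pharmacokinetics part of Section 2.4 reports that terminal-phase "values were 59.1 to 136 hours". Separately it gives 91.3 ± 33.3 h after repeat dosing (n = 23). Sections 2.6.1 and 10.1.1 cite the 91.3 h figure as the reason to sample at steady state. Neither says how T1/2 will be obtained from a 24 h profile. No assay or residual concentration error is given.

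**The concern.** A noncompartmental half-life is ln 2 divided by the slope of log concentration on time in the terminal phase. When the window is a small part of one half-life, the true slope is shallow, and ordinary measurement error is large beside it. Some participants will show a flat or rising line and yield no half-life at all. This happens most often when elimination is slow, so missingness depends on the quantity being compared.

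T1/2 would be tested at the same threshold as Cl and AUC, in small groups. A weak test could be reported as no effect on half-life beside a clearance result that shows an interaction, and a reader would not know which to believe.

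**Working it through.** **Inputs.** Half-life 59.1 to 136 h, and 91.3 ± 33.3 h (Section 2.4). Post-peak samples at 4, 6, 8 and 24 h, plus a Day 22 pre-dose sample (Section 10.1.1). AUC up 38% with ketoconazole and down 77% with rifampin (Section 5.3.1.3). Expected strata of 4–18, 6–18 and 6 (Section 12.2). Concentration error is not in the documents; 5%, 10% and 15% are assumed.

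**Check against the plan's own figures.** Clearance = dose/AUC = 175/41.6 = 4.21 L/h, which reproduces the stated 4.2 L/h. Accumulation is 41.6/7.68 = 5.42. Under one-compartment kinetics, T1/2 = 24 × ln 2 / [−ln(1 − 1/5.42)] ≈ 82 h, close to the stated 91.3 h.

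**Step 1, the window.** With k = ln 2/T1/2, the decline from 4 to 24 h is 1 − exp(−20k).

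| T1/2 (h) | 24 h as share of T1/2 | k (per h) | Decline, 4–24 h |
|---|---|---|---|
| 59.1 | 0.41 | 0.01173 | 21% |
| 91.3 | 0.26 | 0.00759 | 14% |
| 136 | 0.18 | 0.00510 | 10% |

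**Step 2, slope error.** For times 4, 6, 8 and 24 h the mean is 10.5 and Sxx = 42.25 + 20.25 + 6.25 + 182.25 = 251. SE(slope) = error/√251. At 10% error this is 0.10/15.84 = 0.0063 per h, against k = 0.0076. The probability of no positive half-life is Φ(−k/SE).

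| Error | SE/k at 91.3 h | No positive T1/2 at 91.3 h |
|---|---|---|
| 5% | 42% | 1% |
| 10% | 83% | 11% |
| 15% | 125% | 21% |

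At 10% error the loss is 3% at 59.1 h, 11% at 91.3 h and 21% at 136 h, so it is concentrated in slow eliminators. Also at 10% error and 91.3 h, an estimate lies within 25% of the truth when the fitted slope is 0.80 to 1.33 times k: Φ(0.333/0.831) − Φ(−0.20/0.831) = 0.656 − 0.405 ≈ 25%.

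**Step 3, using the pre-dose trough.** At steady state the Day 22 pre-dose sample acts as a second 24 h point. Sxx becomes 397. At 91.3 h and 10% error, SE/k falls from 83% to 66% and the no-half-life share from 11% to about 6.5%. At 5% error SE/k is 33%.

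**Step 4, comparison with real variation.** The between-subject CV is 33.3/91.3 = 36.5%. For the four-point fit, error makes up 57%, 84% and 92% of the variance of the estimated slope at 5%, 10% and 15% error, and 32% at 3%. The share passes one half at an error of about 4.4%.

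**Step 5, power.** This was simulated with one-compartment steady-state dosing, half-life CV 36.5% and a two-sided Mann-Whitney test at 0.05, with 12 versus 12. Columns 3 to 5 are noncompartmental T1/2 at each error level.

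| T1/2 ratio | True T1/2 known | 5% | 10% | 15% |
|---|---|---|---|---|
| 1.38 | 0.52 | 0.21 | 0.08 | 0.07 |
| 0.5 | 0.99 | 0.92 | 0.57 | 0.27 |
| 0.23 | 1.00 | 1.00 | 1.00 | 0.99 |

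The ratios 1.38 and 0.23 carry the ketoconazole and rifampin AUC effects over to T1/2 with volume unchanged. With 6 versus 6 and a ratio of 1.38, power is 0.11, 0.04 and 0.03, against about 0.25 with true T1/2. With no true difference the rejection rate stayed at 0.02 to 0.05, so the damage is lost power and selective loss, not extra false positives.

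**Step 6, the accumulation route.** Taking T1/2 from the ratio of the Day 22 to the Day 1 4 h concentration, error is 4%, 15% and 29% of the variance at 5%, 10% and 15% error. Power for the 1.38 ratio at 12 versus 12 is 0.51, 0.46 and 0.37. This assumes linear one-compartment kinetics and no day-to-day absorption variability.

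**The case against.** The strongest reply is that the plan also permits compartmental methods. Step 6 shows that the scheduled Day 1 and Day 22 samples carry usable half-life information through accumulation. That stands. A reader might infer that the design cannot yield a half-life at all, and the documents do not support this. What remains is that the route is not prespecified, rests on a single post-dose sample on Day 1, and would be blurred by absorption differences between days.

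A reader might also infer that the comparison would mostly measure assay noise. The documents give no assay error. For the four-point noncompartmental fit the statement is true above about 4.4% and false below it, and it does not carry over to the accumulation route.

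Strong induction in Stratum B would shorten T1/2 toward the window and make even the noncompartmental test informative, as the 0.23 row shows. Whether efavirenz or etravirine induces that strongly is not given, and this does nothing for the inhibitor comparison.

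Two further inferences should be resisted. The bioavailability studies in Section 2.4, where "blood samples were collected up to 504 hours post-dose for each subject", were single-dose studies in healthy volunteers and set no standard for continuously dosed patients. The event samples in Appendix I, footnote j, are not washout points: they are taken as close to the event as possible, when dosing may be continuing.

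**Conclusion.** The concern holds for a noncompartmental T1/2. At 91.3 h its slope standard error is about 42%, 83% or 125% of the slope for an assumed error of 5%, 10% or 15%, somewhat better if the pre-dose trough is used. The non-estimable cases fall mainly among slow eliminators. As written, the plan leaves open whether the tested T1/2 will be this estimate or a model-based one.

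It would be wrong to infer that the interaction objective fails. AUC over the dosing interval and Cl/F are estimable from the Day 22/23 samples, and dose escalation (Section 5.2) rests on cycle 1 DLTs, not on pharmacokinetics. This is one unreliable test among three, and it is cheap to remove. The figures assume independent proportional errors and log-linear decline after 4 h; the power figures also assume one-compartment kinetics.

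**What to change.** In Sections 10.1.1 and 12.4:

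- Remove T1/2 from the parameters tested at p<0.05.
- Base the interaction comparison on Cl/F, equivalently dose-normalised AUC over the Day 22/23 interval. Normalising matters because the strata receive different doses.
- Report T1/2 descriptively only, from a named compartmental or accumulation model using the Day 1 and Day 22 samples, and give the number of participants for whom it could not be estimated.
- State how Cl/F is obtained at Level -1 of Stratum A. Dosing there is every other day, so a 24 h profile is not a full dosing interval.

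This changes wording in two sections. It needs no new visits or samples and alters no dosing rule. The cost is that the formal half-life comparison is given up.

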#### 5.3.1.3 Potential drug interactions

CYP450 isozymes:

*In vitro*, XL184 is a substrate of CYP3A4 and a weak substrate of CYP2C9. In healthy volunteers, XL184 AUC increased 38% with co-administration of ketoconazole, a strong inhibitor of CYP3A4, and decreased by 77% with a strong CYP3A4 inducer rifampin. Therefore, avoid chronic use of strong CYP3A4 inducers such as rifampin, dexamethasone, phenytoin, carbamazepine, rifabutin, rifampentin, phenobarbital, and St. John's Wort while taking XL184. Avoid chronic use of strong CYP3A4 inhibitors such as ketoconazole, itraconazole, clarithromycin, indinavir, nefazodone, nelfinavir, and ritonavir. Use alternative medications. **Use of antiretroviral agents that are strong**

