### 12.2 Sample Size/Accrual Rate

No formal statistical hypothesis testing is planned for the primary analysis. Sample size estimates are in agreement with those of a traditional phase I dose escalation 3+3 design. It is expected that the study will enroll approximately 16 to 42 participants across potentially three Strata (Ritonavir or Cobicistat (CYP3A4 inhibitor)-containing HAART [**Stratum A**]; Efavirenz or Etravirine (CYP3A4 inducer)-containing HAART [**Stratum B**]; and Others [**Stratum C**]). Among the expected 16 to 42 enrolled participants, 4 to 18 are expected to be enrolled in Stratum A, 6 to 18 are expected to be enrolled in Stratum B, and 6 participants are expected to be enrolled in Stratum C.

Following the determination of the MTD in each stratum, the MTD dose level for each stratum may be expanded to 6 to 12 participants according to participant availability for further characterization of toxicity, preliminary assessment of response and additional translational study samples. A decision to halt accrual because of lack of participant availability will be at the discretion of CTEP investigators.

The estimated accrual rate for this study is 1 - 2 participants/month.

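### The pharmacokinetic interaction is assessed only by rank-type tests at p<0.05, which have about 15-43% power for the protocol's own inhibitor benchmark; no between-stratum ratio or confidence interval is planned

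*Combined protocol and SAP*

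**What the plan says.** Section 12.4 says that half-life, clearance and AUC "will be compared across relevant antiretroviral therapies using nonparametric statistical testing techniques", and adds "Significance for comparisons will be at the" p<0.05 level. Section 10.1.1 says the same. Neither section names the test, its sidedness or a multiplicity rule. Both plan descriptive statistics, with geometric means and coefficients of variation as examples, by dose level; Section 10.1.1 makes clear that this is within each stratum. Neither plans a ratio between strata, a confidence interval for one, or bounds for no effect.

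On size, Section 12.2 says that "4 to 18 are expected to be enrolled in Stratum A, 6 to 18 are expected to be enrolled in Stratum B", and that "6 participants are expected to be enrolled in Stratum C". Cohorts are 3, extended to 6 after one DLT (Section 5.2), and an MTD level may be expanded to 6 to 12 (Section 12.2). Steady-state samples may be waived (Appendix IV), so groups with PK data can be smaller than enrolment. No power or precision is given for the PK comparison.

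On expected effects, Section 5.3.1.3 reports for healthy volunteers that "XL184 AUC increased 38% with co-administration of ketoconazole, a strong inhibitor of CYP3A4, and decreased by 77% with a strong CYP3A4 inducer rifampin". On variability, Section 2.4 (Pharmacokinetics) gives the AUC CV as "40-43% for the tablet formulation, 43% for the capsule formulation".

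**The concern.** The only stated criterion for objective 1.2.1 is a significance threshold, applied to groups sized for 3+3 escalation. If such a test usually misses an effect as large as the protocol itself cites for a strong CYP3A4 inhibitor, a non-significant comparison of Stratum A with Stratum C carries little information. Nothing in the plan obliges the report to show which ratios the data leave open.

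The synopsis expects higher drug levels on ritonavir or cobicistat, so this is the comparison on which readers will most want a number. What is at stake is how a secondary objective is reported, not the choice of dose in the trial.

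**Working it through.** **The plan's own figure.** Section 12.2 gives a total of 16 to 42. The strata sum to 4 + 6 + 6 = 16 and 18 + 18 + 6 = 42, so it reproduces. It is the only size figure available.

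**Inputs.**
- Effect: AUC ratio 1.38 (inhibitor) and 1 - 0.77 = 0.23 (inducer), Section 5.3.1.3. For apparent clearance the inhibitor ratio inverts to 1/1.38 = 0.72, which is the same distance on the log scale.
- Between-subject CV, Section 2.4: steady-state clearance 4.2 +/- 1.5 L/h gives 1.5/4.2 = 36%; steady-state AUC gives 15.3/41.6 = 37%; the single-dose AUC CV reaches 43%. Range used: 36-43%.
- Log-scale SD = sqrt(ln(1 + CV^2)): 0.349 at 36%, 0.412 at 43%.
- Test: the exact two-sided Wilcoxon rank-sum test at 0.05. The choice of test and two-sidedness are assumptions, because the plan states neither.

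**Smallest attainable p.** The minimum is 2/C(n1+n2, n1). For 3 v 3 this is 2/20 = 0.10; for 3 v 4, 2/35 = 0.057; for 3 v 6, 2/84 = 0.024. Significance is therefore impossible at 3 v 3 and 3 v 4, and possible from 3 v 6.

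**Power for a ratio of 1.38.** Log-normal samples were simulated and compared with the exact critical value. Results are good to about one percentage point.

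| Stratum A v Stratum C | CV 43% | CV 36% |
|---|---|---|
| 3 v 3 | 0% | 0% |
| 3 v 6 | 15% | 19% |
| 4 v 6 | 15% | 20% |
| 6 v 6 | 20% | 26% |
| 12 v 6 | 27% | 36% |
| 18 v 6 (clearance pooled over doses) | 33% | 43% |
| 12 v 12 | 41% | 54% |

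The last row needs Stratum C at twice its expected 6. A three-group Kruskal-Wallis test at 6/6/6, with only Stratum A shifted and CV 40%, has 22% power.

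**Inducer side.** For a ratio of 0.23 the same test has about 98% power or more from 3 v 6 upward, but 0% at 3 v 3 and 3 v 4.

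**What a non-significant result says.** At 6 v 6 the test is non-significant at least 95% of the time when there is no effect. When the true ratio is 1.38 it is non-significant 74-80% of the time (100 - 26 to 100 - 20). The two probabilities differ by a factor of about 1.2 to 1.3 (95/80 to 95/74), so the result barely separates the two cases.

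**What an interval would say.** The 90% limits are the ratio divided and multiplied by exp[t(0.95, n1+n2-2) x SD x sqrt(1/n1 + 1/n2)].
- 6 v 6, CV 43%: 1.812 x 0.412 x sqrt(1/6 + 1/6) = 0.431, a factor of 1.54. An observed 1.38 has limits 0.90-2.12.
- 6 v 6, CV 36%: factor 1.44, limits 0.96-1.99.
- 6 v 6, CV 43%, observed ratio 1.0: limits 0.65-1.54.
- 12 v 6, observed 1.38: upper limit 1.87 (CV 36%) to 1.98 (CV 43%).

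**The case against.** **Phase I PK comparisons are exploratory, and low power comes with a 3+3 design.** True. Section 12.2 sizes the trial for escalation, and an interval adds no participants. But this argues for estimation over an unpowered threshold. Section 12.4 already plans 95% intervals for response rates, so interval estimates are not foreign to the plan.

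**The ingredients are already there.** Geometric means and CVs by stratum and dose level would let a reader build a ratio. This stands in part: what is missing is the commitment to report the ratio and interval, and a stated way to combine dose levels.

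**A reader might infer that a non-significant test will be declared proof of no interaction.** The documents contain no such rule. Misreading is a risk that the plan leaves open, not something it prescribes.

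**A reader might infer that the data could never exclude a doubling.** That is too strong. At 6 v 6 and CV 43%, an observed ratio of 1.0 has an upper limit of 1.54. At 12 v 6 an observed 1.38 has an upper limit below 2 throughout the CV range.

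**A reader might infer that dosing on boosted therapy hangs on this p-value, or that the strata exist for it.** Sections 12.1 and 12.3 use the strata for separate escalation and MTD determination, driven by DLTs. Sections 2.6.1 and 10.1.1 describe the PK comparison as an opportunity that the strata provide.

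**The benchmark may not apply.** The 38% is for ketoconazole in healthy volunteers, and no figure is given for ritonavir or cobicistat. A larger true effect would be easier to find: at 80% power the detectable ratio is about 2.0-2.25 for 6 v 6 and 1.6-1.7 for 12 v 12 (CV 37-43%).

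**Conclusion.** The point holds as a weakness of the inhibitor-side comparison and of its reporting. At the expected Stratum C size, a true ratio of 1.38 would be missed more often than found in every pairing examined: power is about 15-43% from 3 v 6 to 18 v 6, and zero if only 3 v 3 have PK data. Even 12 v 12 is close to a coin toss at 41-54%. An inducer effect near the cited size would be found from 3 v 6 upward, so the criticism does not extend to large inducer effects.

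These figures assume log-normal data, equal CVs of 36-43% in both groups, a two-sided exact rank-sum test, and a comparison of clearance or of AUC at equal or normalised dose. The last matters because Stratum A starts at 20 mg and Stratum C at 60 mg. One-sided testing does not rescue the design: at CV 40% it gives 36% at 6 v 6 and 59% at 12 v 12.

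The documents support saying that a non-significant result would be nearly uninformative and could be misread. They do not support saying that the plan equates non-significance with no interaction, or that the MTD is affected.

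**What to change.** In Sections 10.1.1 and 12.4:
- Make the main interaction result the geometric mean ratio of apparent clearance (or dose-normalised AUC), Stratum A versus C and Stratum B versus C, each with a 90% confidence interval from a log-scale model.
- Keep the rank-test p-values as descriptive only, and name the test.
- State that a non-significant comparison will not be reported as absence of interaction.

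This is a cheap improvement: the same samples and participants, and no change to escalation. Its costs are intervals that will look wide, a log-normal assumption that is hard to check with so few participants, and a routine written amendment with CTEP and IRB approval under Section 14.2. Retaining the rank test as a descriptive check partly offsets the distributional assumption.
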